11.8 Safety Analyses during the Open-Label Extension Period

Safety analyses will follow general considerations in previous sections 11.1 to section 11.7 with the following exceptions:

- Summaries will be provided by visit based on the OLE FAS overall, for the three treatment groups in the OLE period (OLE 2mg, OLE 2mg/3mg, OLE 3mg), and the three

randomized treatment groups in the DB Treatment Period (DB 2mg, DB 3mg, DB placebo).

- Change from Baseline will be summarized using change from OLE Baseline and DB Baseline (refer to Section 4.1).

12 CHANGES TO THE ANALYSIS FROM THE PROTOCOL

Table 4: Summary of Changes to the Analysis from the Protocol

Description of the change	Rationale for change

Original text: Baseline for the Open-Label Extension Period is defined as the last measurement prior to the first etrasimod dose started at Week 24.
 
Changed to: The OLE Period Baseline (OLE Baseline) will be defined as the last nonmissing assessment prior to the first etrasimod dose started at Week 24 for the subject who received placebo during the DB Treatment Period. For subjects who were on etrasimod in the DB Treatment Period, the OLE Baseline will be taken from the DB Baseline.
	
To clarify baseline for the Open-Label Extension Period for safety and efficacy analyses for the OLE Period.

Full Analysis Set (FAS): The FAS includes all randomized subjects in the Randomized Set with a SALT I < 95 at Baseline, irrespective of whether they received any study drug.
 
Changed to The FAS includes all randomized subjects with a SALT I < 95 at Baseline who received at least 1 dose of study drug.
	
To prevent bias in the main analysis of the proportion-based secondary endpoints using non-responder imputation, the randomized subjects who failure to take at least one dose of trial medication will be excluded from the full analysis sets.

The Per Protocol Set consists of all subjects in the FAS who adhere to the protocol.
 
Changed to: The Per Protocol Set consists of all subjects in the FAS with no major protocol deviations potentially having an impact on the SALT I-related primary and secondary efficacy endpoints.
	
To clarify that only subjects with major PDs potentially having an impact on the efficacy endpoints will be excluded from the PPS, not all subjects with at least one PD.

Add OLE Full Analysis Set (OLE FAS):
 
The OLE FAS includes all subjects with a SALT I < 95 at Baseline who received at least one dose of study drug in the Open-Label Extension Period. All efficacy analysis in the OLE Period will be performed over OLE FAS.
	
To be consistent with analysis set with SALT I < 95 for the efficacy analysis in the Double-Blind period. All safety analysis will still be based on OLE Safety Set.

14 APPENDICES

Appendix 1 Output Conventions

TLF will be generated using SAS® and will be displayed on letter size paper with landscape orientation, 1-inch margins and 9 pt Courier New font.

The header section will comprise the Sponsor’s name, the protocol number, the TLF number, the TLF title, the analysis set, and the page number (Page X of Y). The footer section will include the TLF footnotes, the CRO’s name, the reference listing, the delivery description, the data cut-off date (if applicable), the date and time of the execution of the program, and the name of the program.

P-values ≥ 0.0001 will be reported to 4 decimal places; p-values less than 0.0001 will be reported as “<0.0001”; p-values greater than 0.9999 will be reported as “>0.9999”.

Mean, median and quantiles will be displayed to one more decimal place than the original value; minimum and maximum will keep the same number of decimal places as the original value; standard deviation, standard error and CI will be displayed to two more decimal places than the original value. If derived parameters are to be summarized, the number of decimals of the derived values is to be chosen on a case-by-case basis, but the rule above applies. The percent change from baseline for each subject will be derived with 1 decimal and treated as original value.

For categorical summary tables, percentages will be reported to one decimal place. Percentages between 0 and 0.1 (both exclusive) will be displayed as “<0.1”. The denominator for each percentage will be the number of subjects within the population per treatment group unless otherwise specified.

Listings will be ordered by treatment group in DB Treatment Period/OLE Period, subject number, date and visit (where applicable) and timepoint (where applicable). Imputed dates and imputed missing data will not be presented in the listings.

Dates & Times Format

Date and time (if available) will be presented in the format yyyy-mm-dd/hh:mm.

Presentation of Treatment Groups

When applicable, study treatments will be represented as follows in the different outputs:

Data presentation for DB Treatment Period and Full Study

Study Treatment Full Names	Study Treatment Output Names
Etrasimod 2 mg	Etrasimod 2 mg
Etrasimod 3 mg	Etrasimod 3 mg
Placebo	Placebo

Data presentation for OLE Period

DB Treatment Group			OLE Treatment Group			Total
Etrasimod 2 mg	Etrasimod 3 mg	Placebo	Etrasimod 2 mg [^]	Etrasimod 2 mg-3 mg [*]	Etrasimod 3 mg [#]	

[^] Cohort 1 subjects who completed or discontinued from OLE before protocol amendment 2.0/2.1 implementation as well as Cohort 1 and 2 subjects who discontinued from OLE before transitioning to 3 mg .

^{*} Cohort 1 subjects who took 2 mg and transitioned to 3 mg in OLE after treatment initiation.

[#] Cohort 1 subjects who took 2 mg for a week and transitioned to 3 mg in OLE after treatment initiation and Cohort 2 subjects.

Appendix 2 Algorithm for Imputation of Start/End Date of Adverse Events and Prior/Concomitant Medications

Event Start Date Imputation

- Imputation of event end date should be done before imputation of event start date.
- Completely missing: Impute to the first study treatment date.
- Missing day and month: Impute to January 1st, unless year is the same as year of first study treatment dose then impute to the first study treatment date.
- Missing day: Impute to the 1st of the month, unless month and year are the same as month and year of first study treatment dose then impute to the first study treatment date.
- If imputed event start date is after event end date (imputed or not), set the event start date to the imputed event end date.

Event End Date Imputation

- Completely Missing (not flag “ongoing”): Impute to the last contact date.
- Missing day and month: Impute to December 31st, unless year is the same as last contact date then impute to the last contact date.
- Missing day: Impute to the last day of the month, unless year and month are the same as year and month of last contact date then impute to the last contact date.

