5 STATISTICAL CONSIDERATIONS

5.1 Analysis Sets

The following analysis sets will be defined for the DB Treatment Period and OLE Period separately:

Table 2. Summary of Analysis Sets

Analysis Set	Description
DB Treatment Period	
Randomized Set	
The Randomized Set includes all randomized subjects, irrespective of whether they received any study drug.
 
All subjects will be analyzed according to the treatment group to which they were randomized.

Full Analysis Set (FAS)	
The FAS includes all randomized subjects with a SALT I < 95 at Baseline who received at least one dose of study drug. The FAS will be used for the primary analysis of the primary efficacy endpoint and main analysis of the secondary, exploratory, and other efficacy endpoints.
 
All subjects will be analyzed according to the treatment group to which they were randomized.

Modified Full Analysis Set (mFAS)	
The mFAS consists of all randomized subjects with a SALT I < 95 at Baseline who received at least 1 dose of study drug, have a Baseline measurement, and have at least 1 post-randomization measurement.
 
The mFAS is endpoint specific, therefore subjects included in the analysis set for 1 endpoint may differ from another endpoint, based on the Baseline and post-Baseline data. The mFAS will be used for sensitivity analyses for the primary and secondary endpoints in SALT I.
 
All subjects will be analyzed according to the treatment group to which they were randomized.

Analysis Set	Description
Per Protocol Set (PPS)	
The PPS consists of all subjects in the FAS with no major protocol deviations (PD) potentially having an impact on the SALT I-related primary and secondary efficacy endpoints (refer to Sections 7.2 and 10.1).
 
The PPS will be used for sensitivity analyses for the primary and secondary efficacy endpoints in SALT I to evaluate the influence of major PD potentially having an impact on the efficacy endpoints.
 
All subjects will be analyzed according to the treatment group to which they were randomized.

Safety Set (SAF)	
The SAF consists of all randomized subjects who received at least 1 dose of study drug.
 
All safety analysis in the DB Treatment Period will be performed using SAF. All subjects will be analyzed according to the actual treatment they received. In case a subject received more than one actual treatment, the first treatment received will be used for the safety analysis.

OLE Period	

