11.1 Adverse Events

AEs will be coded according to the MedDRA, Version 24.1, and will be summarized overall and by treatment group for across both study periods and for each study period separately.

Treatment emergent adverse events (TEAEs) are defined as any AEs with onset date during or after the first study treatment dose. See Appendix 2 for handling of completely or partially missing dates for AEs. AEs starting on the first study treatment dosing date and related to a pre-dose study assessment will not be considered as TEAE. In the case where it is not possible to define an AE as treatment emergent or not, the AE will be classified as treatment emergent.

Furthermore, TEAEs will be assigned to the DB Treatment Period or OLE Period depending on their onset date – if the AE onset date is before the date of first dose in OLE, the AE will be assigned to the DB Treatment Period AE. If the AE had an onset on or after the date of first dose in OLE, the AE will be assigned to an OLE Period. AEs starting on the Week 24 and related to a pre-dose study assessment will be assigned to DB Treatment Period.

An overall summary table of adverse events will be provided. The number of events and the frequency count and percentage of subjects who experienced an AE, TEAE, TEAE by maximum reported relationship, TEAE by maximum reported Common Terminology Criteria for Adverse Events (CTCAE) severity, serious AE (SAE), serious TEAE, TEAE leading to study drug

discontinuation, TEAE leading to study discontinuation, treatment emergent AE of Special Interest (AESI) and AE leading to death will be presented.

Of note, prior to each database lock (primary and final), AESIs will be flagged as such by the Sponsor Clinical Development/Medical teams from the subset of AEs that will have been classified programmatically as Targeted Medical Events (TMEs) based on an exhaustive list of SOCs and PTs provided by the Sponsor. The list of AEs deemed as AESIs will be finalized prior to each database lock.

Unless otherwise specified, a subject experiencing a TEAE multiple times within the same PT will be counted only once for the corresponding PT. Similarly, if a subject experiencing multiple TEAEs within the same SOC, the subject will be counted only once for that SOC. TEAEs will be sorted by decreasing order of total frequency of SOC and PT within each SOC.

Frequency and percentage of subjects who experience TEAE will be summarized by PT and also by SOC and PT.

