Table 14.3.1.6.1	Summary of Serious Treatment Emergent Adverse Events by System Organ Class and Preferred Term – Double-Blind Treatment Period (Safety Set)
Table 14.3.1.7.1	Summary of Treatment Emergent Adverse Events of Special Interest by Category and Preferred Term - Double-Blind Treatment Period (Safety Set)
Table 14.3.2.4	Listing of Treatment Emergent Adverse Events Leading to Study Discontinuation (Safety Set)
Table 14.3.4.12.1	Incidence of Hepatic Enzyme Elevations by Visit - Double-Blind Treatment Period (Safety Set)
Table 14.3.4.13.1	Incidence of Absolute Lymphocyte Count Decrease - Double-Blind Treatment Period (Safety Set)
Table 14.3.5.2	Summary of Vital Signs Cardiac Monitoring I - Full Study (Safety Set)

Primary Analysis – Batch 2

Table Number	Table Title
Table 14.1.1.0	Study Information
Table 14.1.1.1.1	Subject Disposition - Screening (All Subjects)
Table 14.1.1.2.1	Analysis Sets – Double-Blind Treatment Period (Randomized Set)
Table 14.1.2.1	Demographic and Baseline Characteristics - Double-Blind Treatment Period (Randomized Set)
Table 14.1.2.3	Demographic and Baseline Characteristics - Double-Blind Treatment Period (Safety Set)
Table 14.1.3.1.1	Important Protocol Deviations - Double-Blind Treatment Period (Randomized Set)
Table 14.1.3.2.1.1	Major Protocol Deviations - Double-Blind Treatment Period (Randomized Set)
Table 14.1.3.2.1.2	Major Protocol Deviations Leading to the Exclusion from the Per Protocol Set - Double-Blind Treatment Period (Randomized Set)
Table 14.1.3.3.1	Protocol Deviations Associated to COVID-19 - Double-Blind Treatment Period (Randomized Set)
Table 14.1.4.1	Surgical and Medical History (Safety Set)
Table 14.1.4.2.1	Alopecia Areata Disease History (Safety Set)
Table 14.1.4.2.2	Alopecia Areata Disease History (Full Analysis Set)
Table 14.1.5	Prior Medications - Double-Blind Treatment Period (Safety Set)
Table 14.1.6.1	Concomitant Medications - Double-Blind Treatment Period (Safety Set)
Table 14.1.7.1	Study Treatment Exposure and Compliance - Double-Blind Treatment Period (Safety Set)
Table 14.2.1.3.2	Subgroup Analysis: Summary of SALT I Score - Observed Cases - Double-Blind Treatment Period - Sex (Full Analysis Set)
Table 14.2.1.3.3	Subgroup Analysis: Summary of SALT I Score - Observed Cases - Double-Blind Treatment Period - Race (Full Analysis Set)
Table 14.2.1.3.4	Subgroup Analysis: Summary of SALT I Score - Observed Cases - Double-Blind Treatment Period - Age (Full Analysis Set)

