Table 14.1.3.2.2	Major Protocol Deviations – Open-Label Extension Period (Open-Label Extension Safety Set)
Table 14.1.3.2.3	Major Protocol Deviations – Full Study (Randomized Set)
Table 14.1.3.3.2	Protocol Deviations Associated to COVID-19 – Open-Label Extension (Randomized Set)
Table 14.1.3.3.3	Protocol Deviations Associated to COVID-19 – Full Study (Randomized Set)
Table 14.1.6.2	Concomitant Medications - Open-Label Extension Period (Open-Label Extension Safety Set)
Table 14.1.6.3	Concomitant Medications – Full Study (Safety Set)
Table 14.1.7.2	Study Treatment Exposure and Compliance - Open-Label Extension Period (Open-Label Extension Safety Set)
Table 14.1.7.3	Study Treatment Exposure and Compliance - Full Study (Safety Set)
Table 14.2.8	Summary of Change and Percent Change from Baseline in SALT I Score - Open-Label Extension Period (Open-Label Extension Full Analysis Set)
Table 14.2.9	Summary of Proportion of Subjects Achieving Improvement in SALT I - Observed Cases – Open-Label Extension Period (Open-Label Extension Full Analysis Set)
Table 14.2.10	Summary of Change from Baseline in AASIS – Observed Cases - Open-Label Extension Period (Open-Label Extension Full Analysis Set)
Table 14.2.11	Summary of Change from Baseline in AA-QLI – Observed Cases - Open-Label Extension Period (Open-Label Extension Full Analysis Set)

Table Number	Table Title
Table 14.2.12	Summary of Change from Baseline in Peripheral Lymphocyte Count – Observed Cases - Open-Label Extension Period (Open-Label Extension Full Analysis Set)
Table 14.2.13	Summary of Proportion of Subjects Achieving a SALT I Score ≤ 10 and ≤ 20 – Observed Cases - Open-Label Extension Period (Open-Label Extension Full Analysis Set)
Table 14.3.1.1.2	Overall Summary of Adverse Events - Open-Label Extension Period (Open-Label Extension Safety Set)
Table 14.3.1.1.3	Overall Summary of Adverse Events - Full Study (Safety Set)
Table 14.3.1.2.2	Summary of Treatment Emergent Adverse Events by System Organ Class and Preferred Term - Open-Label Extension Period (Open-Label Extension Safety Set)
Table 14.3.1.2.3	Summary of Treatment Emergent Adverse Events by System Organ Class and Preferred Term - Full Study (Safety Set)
Table 14.3.1.3.2	Summary of Treatment Emergent Adverse Events by Preferred Term - Open-Label Extension Period (Open-Label Extension Safety Set)
Table 14.3.1.3.3	Summary of Treatment Emergent Adverse Events by Preferred Term – Full Study (Safety Set)

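### Full-study adverse-event tables keep the double-blind arm names, so events on open-label etrasimod are counted under Placebo

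*SAP*

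**What the plan says.** **Column names.** SAP Appendix 1 (Presentation of Treatment Groups) heads its first scheme "Data presentation for DB Treatment Period and Full Study" and lists three output names: Etrasimod 2 mg, Etrasimod 3 mg and Placebo. A second scheme, showing double-blind group, extension group and a total, is given for extension-period outputs only.

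**Pooling.** SAP 11.1 has adverse events "summarized overall and by treatment group for across both study periods and for each study period separately". It defines treatment-emergent events as "any AEs with onset date during or after the first study treatment dose", with no cut at the start of the extension.

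**Tables.** The Final Analysis list in SAP Appendix 3 has Full Study (Safety Set) tables for:
- the overall adverse-event summary (14.3.1.1.3)
- events by system organ class and preferred term (14.3.1.2.3), preferred term (14.3.1.3.3), relationship (14.3.1.4.3) and severity (14.3.1.5.3)
- serious events (14.3.1.6.3) and events of special interest (14.3.1.7.3)
- vital-sign cardiac monitoring (14.3.5.2 and 14.3.5.3) and ECG cardiac monitoring (14.3.6.1.3.1 and 14.3.6.1.3.2).

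Table 14.3.5.2 is also in Primary Analysis Batch 1.

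**Assignment.** For the Safety Set, SAP 5.1 Table 2 says: "In case a subject received more than one actual treatment, the first treatment received will be used for the safety analysis".

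**Treatment after Week 24.** The Protocol Synopsis (Reference Therapy) states that the extension has no placebo arm. Under SAP 3.1 and 3.3, all subjects who enter it take etrasimod.

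**The concern.** A table column headed Placebo is normally read as time without drug. Here a serious or special-interest event on open-label etrasimod would be printed in that column if the subject began on placebo. The 2 mg column has the same problem: it collects events on 3 mg in subjects who transition.

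These are the only adverse-event tables that span the whole study, and long-term safety is a secondary objective (SAP 2.1.2). A reader comparing the columns would see a smaller excess on etrasimod than there was, with no sign that much of the comparator's exposure was to active drug.

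**Working it through.** The plan gives no figure of its own on this point, so the check traces the rules and then sizes the effect on the planned design.

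**1. Tracing one subject.** A subject randomised to placebo completes Week 24, starts etrasimod and has a serious event at Week 30. By SAP 11.1 the event is treatment-emergent and belongs to the extension period, so it is absent from the double-blind table. In the extension table it appears under both the double-blind group and the extension group. In the Full Study table the only names on offer are the three double-blind ones, and the Safety Set rule points to the first treatment received. The event is counted under Placebo.

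**2. Exposure in the full-study Placebo column.** Inputs are the period lengths of 24 and 28 weeks (SAP 3.1), and the allocation and 15% drop-out (SAP 3.2).
- Planned placebo subjects: 36 × 1/3 + 42 × 2/7 = 12 + 12 = 24.
- No drop-out: placebo 24 × 24 = 576 person-weeks; etrasimod 24 × 28 = 672. Share on etrasimod: 672/1,248 = 53.8%, the same as 28/52 for one completer.
- 15% do not enter, all entrants complete: 0.85 × 24 = 20.4 entrants; etrasimod 20.4 × 28 = 571.2.
  - Non-entrants leave at Week 12 (assumed): placebo 20.4 × 24 + 3.6 × 12 = 532.8; share 571.2/1,104.0 = 51.7%.
  - Non-entrants leave at Week 24 (assumed): placebo 576; share 571.2/1,147.2 = 49.8%.
- Wider assumptions (0-50% not entering, mean extension time 14-28 weeks): 23% to 54%.

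**3. The 2 mg column.** A completer who moves to 3 mg at Week 25 spends 27 of 52 weeks (52%) on 3 mg. The share is lower for Cohort 1 subjects who transition later, and zero for those who stay on 2 mg.

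**4. Effect on a risk comparison (assumed rates).** Let p_P and p_E be 24-week incidences on placebo and etrasimod, with constant hazards. All subjects are followed to Week 24, 85% enter the extension, and entrants complete it. The incidence in a column whose double-blind incidence is p is

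1 − (1 − p) × [0.15 + 0.85 × (1 − p_E)^(28/24)].

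| p_P | p_E | Double-blind ratio | Full-study Placebo | Full-study etrasimod | Full-study ratio | Risk difference, double-blind to full study |
|---|---|---|---|---|---|---|
| 10% | 20% | 2.0 | 27.5% | 35.6% | 1.29 | 10.0 to 8.1 points |
| 5% | 15% | 3.0 | 18.9% | 27.5% | 1.45 | 10.0 to 8.5 points |
| 10% | 10% | 1.0 | 18.8% | 18.8% | 1.0 | 0 to 0 |

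For the first row: 0.80^(28/24) = 0.771; the bracket is 0.15 + 0.85 × 0.771 = 0.805; Placebo is 1 − 0.90 × 0.805 and etrasimod is 1 − 0.80 × 0.805. Had the control subjects stayed on placebo, their column would read 18.8% (third row), a ratio of 35.6/18.8 = 1.89. Most of the fall from 2.0 to 1.29 is therefore the crossover, not the longer follow-up.

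**5. Cardiac monitoring.** SAP 11.3 and 11.5 summarise these data at nominal Day 1 and Week 24, so the two visits are not pooled. The cardiac-monitoring tables for the heart-rate categories (below 40 and below 50 bpm) are listed in Appendix 3 only as Full Study tables. At Week 24 the Placebo column holds a first-ever etrasimod dose, while the other columns hold subjects with up to 24 weeks of exposure. Protocol 1.2 states that the heart-rate reduction is greatest on the first day of dosing.

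**The case against.** The strongest reply is that nothing important rests on these tables. SAP 11.1 also requires each period to be summarised separately. Appendix 3 lists double-blind-only tables for every adverse-event category above, and extension-only counterparts in the layout that shows both groupings. No test, interval or ratio is planned for adverse events. All of that stands. A reader might infer that the blinded safety comparison is biased, or that the long-term safety objective cannot be met. The documents do not support either inference.

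Second, the Appendix 1 block maps names and is prefaced as applying where relevant. Table shells are in a separate document (SAP 4), which could carry a footnote or a sequence label. That is possible, but nothing in the SAP specifies one.

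Third, the first-treatment rule sits in the double-blind part of SAP Table 2. Applying it to Full Study tables is an inference from their naming the Safety Set. The inference is reasonable, and without it Appendix 1 still offers only the three names.

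Fourth, a reader might infer that the cardiac tables are diluted too, or that every former placebo subject moves to 3 mg. Neither holds. The cardiac data are by visit. Some Cohort 1 subjects may stay on 2 mg (Protocol 3.1), and others finish or stop before any transition (SAP Appendix 1 footnotes).

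**Conclusion.** The point holds for the Full Study adverse-event tables. Followed as written, the SAP counts open-label etrasimod events under Placebo, and 3 mg events under Etrasimod 2 mg for subjects who transition. The 54% exposure share for a completer follows from the design. The 50-52% figure rests on 15% not entering and no extension attrition; with attrition it can be much lower. The ratios in the table above rest on assumed rates and constant hazards. The direction, toward no difference, holds for any risk that the drug raises.

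For the cardiac-monitoring tables the fault is one of labelling. Severity is moderate: the tables are descriptive, and the double-blind-only and extension-only outputs remain correct.

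**What to change.** **Adverse events.** In SAP Appendix 1 and the Full Study adverse-event tables, do one of the following:
- attribute each event to the treatment being taken at onset (placebo, etrasimod 2 mg, etrasimod 3 mg, any etrasimod), with subject-years per column; or
- label columns by sequence (for example, placebo then etrasimod) and restrict any column headed Placebo to double-blind time.

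**Cardiac monitoring.** Keep the double-blind grouping, and label the Week 24 rows as first etrasimod dose (former placebo) versus continued dosing. Grouping by current treatment would be wrong here: subjects entering the extension start on 2 mg, so first-ever and continued dosing would merge into one column.

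**Cost.** SAP wording and some reprogramming; no new data. Protocol 11.9.3 already plans total subject-years. Under the at-onset option a subject can appear in more than one column, and first-week events in the 3 mg arm fall under 2 mg because of the lead-in week. Subject-years should be summed over actual dosing intervals. The first-to-last-date formula in SAP 9 would give a completing Cohort 2 subject in the 3 mg arm about 25 weeks on 2 mg, when the schedule has 2 (Week 1, and Week 24 to 25).
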